**2. PARTICIPANTS:**

a. RECRUITMENT

Participants will be recruited at 2-3 months of age through Pediatric Associates, PSC, a pediatrician practice that has 3 locations in northern Kentucky. If adequate enrollment cannot be achieved through Pediatric Associates, an amendment will be submitted to expand recruitment

to include daycares, Sona system (i.e., student participants can enroll if they have a child meeting study inclusion criteria), and internet and social media sites for our research lab (i.e., The Healthy Kids Lab).

1) Number of participants

The study will enroll 40 total participants. Twenty participants will be randomized to receive the study treatment and 20 participants will be randomized to the control group.

(b) Rationale

This number of participants was determined based on the number of participants feasible to enroll as part of a pilot study while still generating enough data regarding treatment feasibility.

2) Inclusion and exclusion criteria

Participants will be infants aged 3-9 months and their families ( $n = 40$ ). Infants with both normal and elevated weight-for-length will be enrolled. Inclusion criteria include 1) infant has not previously been introduced to complementary foods (i.e., any food besides formula or breastmilk), 2) infant does not have a known developmental delay, 3) infant does not have impaired fine or gross motor skills (which would impact ability for self-feeding), 4) infant does not have a condition currently impacting their feeding and eating, 5) infant born at  $\geq 38$  weeks gestation, 6) infant current weight-for-length  $\geq 10^{\text{th}}$  percentile (Infants with suboptimal growth will be excluded due to potential safety implications of modifying eating and feeding styles of infants with growth difficulties), and 7) parent is a fluent English speaker (because this is the language the intervention will be delivered in).

3) Vulnerable participants

(a) Vulnerability

All study participants will be children less than 1 year old.

(b) Rationale

The objective of the current study is to test an intervention for healthy infant feeding. Therefore, all participants are required to be infants.

(c) Confirmation

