A trained research assistant or study PI will complete the informed consent process with a parent/legal guardian of each participant. During that process, the research assistant will confirm that the legal guardian is 18 years of age or older by asking parents to self-report age if they are a young adult believed to be close to 18 years of age. During the consent process, they will also inform the study PI if they have any concerns about a participant's cognitive ability to consent.

4) Risks and discomforts from participating

(a) Type and level of risk or discomfort

Risk or Discomfort	Level
Parental emotional discomfort (anxiety, nervousness) related to introducing their children to solid foods.	minimal
Child risk for choking during introduction of solid foods.	minimal

However, prior research has demonstrated that infant self-feedings are not associated with increased risk of choking (Fangupo et al., 2016).	
Child risk for growth faltering. However, prior research has demonstrated that children introduced to solid foods incorporating self-feeding are not at increased risk for growth faltering in comparison to other children (Townsend & Pitchford, 2012).	minimal

(b) Safety monitoring plan

Despite no greater than minimal risk to participants, we will still actively assess for adverse events related to growth faltering and choking. At each intervention session or study visit, study participants will report on if there were any choking episodes since the last meeting. Additionally, child weight will be measured, with any child failing to gain weight since the last session defined as an adverse event. Between sessions or meetings, parents will be advised to call 911 immediately if their child experiences a choking episode. Participants will also be informed to contact the study PI if there is any concern regarding their child's weight gain or after a choking episode occurs. Any reports of choking episodes provided either at study visits or between study visits will be recorded on the Choking Incident Form. All reported adverse events will be assessed by the study PI.

(c) Reporting

Research assistants collecting adverse event information at study visits and intervention sessions will report this information directly to the PI. Between visits and sessions, study participants will be asked to communicate to the study PI directly if they have any concerns about study participation or if their child experiences an adverse event.

(2) Notification of IRB

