Study participants will be assigned to either the control or treatment condition at their first study visit following completion of informed consent and baseline measures. A computer-generated random number list will be used to determine condition assignment for each participant. Participants will be notified immediately at the study visit of their study condition.

(b) Activities and duration

The first study appointment will occur when the infant is 3 months of age (defined as 3 months 0 days – 3 months 30 days) at the Schubert Research Clinic (SRC) at CCHMC. The infant and at least one parent will attend the appointment. The appointment will begin with completion of the informed consent process with the study PI or trained research assistant. Next, participants will

complete study measures, including infant anthropometrics and parent-report measures of demographics, parental feeding practices and beliefs, and infant appetite. Families will also receive information about how to intervene if their child experiences a choking incident while introducing complementary foods. Following completion of study measures, families will be randomized to either the control or treatment condition using a computer-generated random number list. Participants will receive \$50 for completion of this visit. Participants in the intervention condition will be instructed to not introduce their child to complementary foods prior to their first Treatment Session at 4 months of age. All families will receive safety information regarding monitoring infant growth and choking.

Participants assigned to the treatment condition will attend 3 intervention sessions at the Healthy Kids Lab, located in the Edwards Center on UC campus. The sessions will be scheduled with individual families when the child is 4 months (+/- 30 days), 6 months (+/- 30 days), and 9 months (+/- 30 days) of age. An attendance log of whether participants attend treatment will be kept.

All participants will also complete a final study visit at the SRC at CCHMC when the child is 9 months (+/- 30 days) of age. They will complete a final study visit to complete post-treatment period measurements, which will include infant anthropometrics and parent-report of infant appetite, infant diet, and parental feeding practices and beliefs. Families receiving the intervention will also complete a measure of treatment satisfaction. Participants will receive \$50 for completion of this visit.

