**(c) Data collection tools**

Infant Anthropometrics. Anthropometrics will be measured for pre-post analyses at both the initial and final study visit by Bionutrition Core staff at the SRC. Infant length will be measured in triplicate to the nearest 0.1 centimeter using an infant length board (O'Leary, Ellard Instrumentation, LTD). Weight will be measured in triplicate to the nearest 100 grams with the infant in a dry diaper using a Scale Tronix 4802 digital infant/pediatric scale. The average of the three measurements will be used to calculate weight for recumbent length. Percentiles for each infant's weight for recumbent length will be obtained using sex and age specific World Health Organization (WHO) growth charts. Information will be recorded on the "Anthropometrics Form".

For families in the intervention condition, infants will also have length and weight measured at each treatment session to monitor safety of growth. Measurements will be taken by study interventionists using a SECA infant length board (SECA 416) and SECA infant digital scale (SECA 374).

Infant and Family Demographics. Demographics information will be collected at the initial study visit using a form created for use in this study.

Treatment Satisfaction. Caregivers in the treatment condition will complete a survey to provide quantitative and qualitative feedback on the intervention after the final treatment session. The questionnaire includes Likert scale ratings of the appropriateness, helpfulness, and timeliness of session content as well as open-ended questions for the parent to provide qualitative feedback on ways to improve the intervention (e.g., additional content to cover).

Infant Appetite. Parents will complete a survey entitled the *Baby Eating Behaviour Questionnaire* (Llewellyn et al., 2010) at both the initial study visit and final study visit or final treatment visit to assess current infant appetite. Parents respond to 17 items on a 5-point scale. Scores for "Enjoyment of Food", "Food Responsiveness", "Slowness in Eating", and "Satiety Responsiveness" are calculated.

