College of Arts and Sciences
Department of Psychology
University of Cincinnati
Cincinnati, OH, 45221

Official Title: Healthy Start to Feeding Pilot Trial

Brief Title: Healthy Start to Feeding Intervention

NCT Number: NCT03597061

Document Date: 7/9/2018

Date Uploaded: 6/24/21

Document: Statistical Analysis Plan

Statistical Analysis Plan

Primary Aim (Examine the impact of the HSF intervention on growth trajectories, appetite regulation, and diet at post-treatment) was explored through group comparisons between the control and treatment groups on weight-for-length scores, subscale scores of the BEBQ, and number of fruits and vegetables consumed in the last week as assessed on a food frequency questionnaire. Prior to between group comparisons, potential differences between the control and treatment group on key sociodemographic and baseline variables (e.g., gender, baseline weight-for-length, household income, caregiver education level) were explored to confirm the effectiveness of randomization to treatment condition. A series of Analysis of Variance (ANOVA) were computed to examine whether the control and treatment groups differed on outcome variables.

Secondary Aim (Determine the feasibility of the HSF intervention and family satisfaction with the treatment) was explored using descriptive analyses. We calculated the average number of treatment sessions attended and the percentage of participants that attended 2 (67%) and 3 (100%) of the sessions. Additionally, we calculated the percentage of caregivers who either “somewhat agree” or “strongly agree” that the intervention was appropriate, timely, helpful, and satisfactory as assessed by the Treatment Satisfaction Survey. Qualitative comments on the Treatment Satisfaction Survey were also reviewed to identify themes regarding additional information to include in the intervention, what information was most helpful, what caregivers would like to see changed about the intervention, and what they would like to see stay the same.

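### The only defined growth adverse event is absence of weight gain, and no analysis counts infants with low weight-for-length, so a shift into the low tail would not show in the planned results

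*Protocol*

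**What the plan says.** Section 2.a.4 of the protocol lists growth faltering among the risks, rates it minimal, and says it will be actively assessed. The safety monitoring plan, 2.a.4(b), gives the only definition of a growth event: "child weight will be measured, with any child failing to gain weight since the last session defined as an adverse event". It adds a route through the parents: "Participants will also be informed to contact the study PI if there is any concern regarding their child's weight gain". Under available resources, families are also referred to the child's pediatrician. Under other notification, families are to be told at once if the intervention is judged to raise the risk of growth faltering.

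At entry the protocol judges growth differently. The inclusion criteria (2.a.2) require weight-for-length at or above the 10th percentile, for a stated safety reason: "Infants with suboptimal growth will be excluded due to potential safety implications of modifying eating and feeding styles of infants with growth difficulties".

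Under data collection tools (Infant Anthropometrics), treatment-arm "infants will also have length and weight measured at each treatment session to monitor safety of growth". The sessions fall "when the child is 4 months (+/- 30 days), 6 months (+/- 30 days), and 9 months (+/- 30 days) of age". Control infants are measured only at the first and final visits at the research clinic.

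Aim 2 H1 predicts a lower incidence of weight-for-length at or above the 85th percentile. Protocol section 4 and the SAP, which makes this the primary aim, plan "group comparisons between the control and treatment groups on weight-for-length scores" by ANOVA. Neither includes a category or summary for low weight-for-length.

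**The concern.** The protocol uses one measure of poor growth to decide who may safely enter and another to decide what counts as a growth event afterwards. The second depends only on the sign of the weight change. It takes no account of the time elapsed, the length gained or the change in percentile. Length is collected at sessions for safety, yet no rule uses it.

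The intervention aims to raise satiety responsiveness and lower food responsiveness, so any harm to growth would lie in the same direction as the intended effect. A lower mean weight-for-length can come from fewer high infants, from more low infants, or from both, and the planned comparison of means does not separate them. At stake is a report that reads a lower mean favourably and states that no growth adverse events occurred, when neither result would have shown movement into the low tail. The promise to tell families of an increased risk also needs some between-arm summary of low growth, and none is planned.

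**Working it through.** The plan states no figure for this point. The sample size is set by feasibility, with no effect size, SD or power, so there is nothing to reproduce. The check is of the logic, followed by an illustration of size.

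**1. What the rule can detect.** An event requires weight gain of zero or less since the last measurement. With windows of ±30 days, session 2 can fall at about 5 months and session 3 at about 10 months, a gap of up to 10 − 5 = 5 months. For controls, the first visit is at 3 to about 4 months and the final visit at about 8 to 10 months. Their single interval is therefore about 8 − 4 = 4 to 10 − 3 = 7 months. Any positive gain over these spans passes.

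**2. How far an infant could fall without an event.** The documents give no reference values, so these are assumptions:
- weight at a given length is normal, with CV 7–10% of the median;
- the reference median rises by g = 5–30% as the infant lengthens;
- the infant's own weight rises in total by e = 1–5%, with some gain in every interval.

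Starting weight relative to the median: w0 = 1 + z0 × CV. End z-score: z1 = [w0 × (1 + e)/(1 + g) − 1]/CV.

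With CV = 8.5%, e = 2%, g = 20%:
- Start at the 50th percentile: w0 = 1; 1.02/1.20 = 0.850; z1 = −0.150/0.085 = −1.76, about the 4th percentile.
- Start at the 10th (z0 = −1.28): w0 = 0.891; 0.891 × 1.02/1.20 = 0.757; z1 = −0.243/0.085 = −2.85, about the 0.2nd percentile.

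Other values of g, with the same CV and e:

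| Rise in reference median | From the 50th, ends at | From the 10th, ends at |
|---|---|---|
| 5% | 37th | 5.7th |
| 10% | 20th | 2nd |
| 20% | 4th | 0.2nd |
| 30% | 0.6th | 0.02nd |

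For the 50th-percentile starter with a 20% rise, the range over CV 7–10% and e 1–5% is the 1.2nd to the 10.6th percentile. With only a 5% rise, the median infant stays well above the 10th. When e equals g (both 5%), no percentile changes.

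**3. Effect on the planned ANOVA.** Assume that scores are z-scores and that all 20 infants in the arm are measured. The shift in the arm mean is (number of infants × fall)/20. One infant falling 2 to 3 z shifts it by 2/20 = 0.10 to 3/20 = 0.15 z. Three such infants shift it by 6/20 = 0.30 to 9/20 = 0.45 z. In each case the mean goes down.

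**4. Effect on H1.** A fall from the 50th to the 1st percentile leaves the incidence at or above the 85th unchanged. Only an infant who would otherwise have been at or above the 85th changes it, by 1/20 = 5 percentage points.

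**5. What a low-tail count can show.** With 0 of 20 infants below the 10th percentile, the exact two-sided 95% upper limit is 1 − 0.025^(1/20) = 0.168, about 17%.

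**The case against.** The strongest reply is that an entry criterion and an on-study trigger may legitimately differ. That is right. A reader might infer that the 10th percentile is a safety limit throughout the study and that the rule breaches it. The documents apply it only at entry and do not say whether it continues. The gap is that they are silent, and that length collected for safety has no stated use.

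Second, low growth need not go unnoticed. Parents are told to report concerns, the pediatrician is available, and WHO percentiles are obtained at the first and final visits. This stands. However, the parent route has no threshold, and the percentiles feed no low-tail summary.

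Third, a reader might infer that a fall in percentile is simply counted as benefit. That is too strong. Under H1 a very low infant is a non-case, exactly like a healthy one, and the ANOVA text asks only whether the groups differ. What stands is that the fall moves the mean in the hoped-for direction and nothing offsets it.

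Fourth, a reader might infer that the rule would miss most growth faltering, or that one 100 g step would always clear it. The documents say nothing about how faltering usually presents. The 100 g precision is stated only for the clinic scale at the study visits, not for the session scale.

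Finally, a percentile trigger added to the adverse event definition would be a clinical rule. It would also be checked up to four times after baseline in treatment infants (three sessions and the final visit) but once in controls, so chance crossings alone would favour more flags in the treatment arm. This stands, and no such trigger is proposed here.

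**Conclusion.** The point holds in a limited form. From the text alone, the sole defined growth event ignores length and percentile, an infant can drop below the protocol's entry threshold without meeting it, and neither section 4 nor the SAP summarises low weight-for-length. No reference data are needed for that. The size of any fall does rest on assumed values and ranges from negligible to severe; infants who enter near the 10th percentile have the least room. The documents do not show that such falls will occur, and they contain no stated on-study limit. The consequence is one of interpretation: a lower mean weight-for-length together with no growth adverse events would not by itself rule out movement into the low tail. This should be corrected, because the growth comparison belongs to the SAP's primary aim and the data needed are already specified.

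**What to change.** 1. In protocol section 4 and the SAP, add one descriptive row: by arm, the number and proportion of infants below the 10th weight-for-length percentile at the final research-clinic visit, with exact confidence intervals. Place it beside the weight-for-length comparison, and do not interpret a lower mean as benefit without it. That visit uses the same procedure in both arms. The SAP is written in the past tense; if outcome data have already been examined, label the row as post hoc.

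2. Reconcile the safety monitoring plan with the inclusion criteria and the Infant Anthropometrics text. State whether the entry-level growth concern applies after enrolment, and how the session lengths and weights are used. Any clinical threshold or response is for the investigator and the pediatrician to decide.

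3. State that growth flags arising at sessions are not to be compared between arms, because control infants are not measured at sessions.

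The cost is one table row from data already collected and a few sentences in the safety section. The drawback is imprecision: at 20 per arm the row describes and cannot establish the absence of harm.

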**3. RESEARCH-RELATED ACTIVITY:**

a. SECONDARY ANALYSIS of an EXISTING DATASET

Not applicable.

b. REVIEW OF RECORDS that were collected for NON-RESEARCH PURPOSES  
Not applicable.

c. RESEARCH ACTIVITIES

1) Privacy of participation

It is not necessary to keep the fact that an individual is participating private. A person participating in this study is only an indicator that they have an infant, and does not disclose anything else about the person that needs to be kept private.

2) Confidentiality of data

Data will be kept private by using a study ID number instead of the participant's name on the research forms. We will keep a master list of names and study ID numbers in a separate location from the research forms. We will limit access to research data to the research team. Participants' identities and information will be kept confidential unless the authorities have to be notified about abuse or immediate harm that may come to the participant or others (e.g., report of child abuse to Child Protective Services).

Data will be kept in [name] research lab at UC. Paper copies of data will be kept in a locked filing cabinet in the PI's research lab at UC, and electronic data will be stored on either password protected computers or a secure network drive. Audio recording of treatment sessions will be stored electronically on the secure UC network drive. These will be stored in a separate folder from any other participant data or names. Only study staff will have access to these recordings. The document linking study ID numbers to participant names and the consent forms will be stored separately from study data. All data will be de-identified following completion of study analyses and publication with the exception of the document linking study ID numbers to participant names and the audio recordings, which cannot be deidentified based on the nature of the data. Paper copies of data, consent forms, and the document linking study ID numbers to participant names will be destroyed through secure shredding 5 years following the last publication of study results in compliance with American Psychological Association recommendations. The data from this research study may be published; but participants will not be identified in publications.

3) Research-related activities

(a) Participant cohorts

Study participants will be assigned to either the control or treatment condition at their first study visit following completion of informed consent and baseline measures. A computer-generated random number list will be used to determine condition assignment for each participant. Participants will be notified immediately at the study visit of their study condition.

(b) Activities and duration

The first study appointment will occur when the infant is 3 months of age (defined as 3 months 0 days – 3 months 30 days) at the Schubert Research Clinic (SRC) at CCHMC. The infant and at least one parent will attend the appointment. The appointment will begin with completion of the informed consent process with the study PI or trained research assistant. Next, participants will

complete study measures, including infant anthropometrics and parent-report measures of demographics, parental feeding practices and beliefs, and infant appetite. Families will also receive information about how to intervene if their child experiences a choking incident while introducing complementary foods. Following completion of study measures, families will be randomized to either the control or treatment condition using a computer-generated random number list. Participants will receive \$50 for completion of this visit. Participants in the intervention condition will be instructed to not introduce their child to complementary foods prior to their first Treatment Session at 4 months of age. All families will receive safety information regarding monitoring infant growth and choking.

Participants assigned to the treatment condition will attend 3 intervention sessions at the Healthy Kids Lab, located in the Edwards Center on UC campus. The sessions will be scheduled with individual families when the child is 4 months (+/- 30 days), 6 months (+/- 30 days), and 9 months (+/- 30 days) of age. An attendance log of whether participants attend treatment will be kept.

All participants will also complete a final study visit at the SRC at CCHMC when the child is 9 months (+/- 30 days) of age. They will complete a final study visit to complete post-treatment period measurements, which will include infant anthropometrics and parent-report of infant appetite, infant diet, and parental feeding practices and beliefs. Families receiving the intervention will also complete a measure of treatment satisfaction. Participants will receive \$50 for completion of this visit.

